Appendix I: Threshold Criteria for Clinical Chemistry and Hematology

Threshold Criteria for Clinical Chemistry and Hematology

Parameter	Threshold Criteria	Comments
Clinical Chemistry		
CPK	>ULN - ≤ 2.5 x ULN >2.5 - ≤ 5 x ULN >5 - ≤ 10x ULN >10 x ULN	CTCAE grades 1-4
Creatinine	>ULN - ≤ 1.5 x ULN >1.5 - ≤ 3.0 x ULN >3.0 - ≤ 6.0 x ULN >6.0 x ULN	CTCAE grades 1-4
Blood Urea Nitrogen	>ULN - ≤ 1.5 x ULN >1.5 - ≤ 3.0 x ULN >3.0 - ≤ 6.0 x ULN >6.0 x ULN	Same criteria as creatinine No CTCAE
Sodium	Hyponatremia <LLN - ≥130 mmol/L <130 - ≥120 mmol/L <120 mmol/L Hypernatremia >ULN - ≤ 150 mmol/L >150 mmol/L - ≤155 mmol/L >155 mmol/L - ≤ 160 mmol/L >160 mmol/L	CTCAE grade 1, 3, 4 (No CTCAE grade 2) CTCAE grade 1-4
Potassium	Hypokalemia <LLN - ≥ 3.0 mmol/L <3.0 - ≥ 2.5 mmol/L <2.5 mmol/L Hyperkalemia >ULN - ≤ 5.5 mmol/L >5.5 - ≤ 6.0 mmol/L >6.0 - ≤ 7.0 mmol/L >7.0 mmol/L	CTCAE grade 1&2, 3, 4 (Grade 1 and 2 are the same) CTCAE grade 1-4
Total Cholesterol	>ULN - ≤ 7.75 mmol/L >7.75 - ≤ 10.34 mmol/L >10.34 - ≤ 12.92 mmol/L >12.92 mmol/L	CTCAE grade 1-4
Triglycerides	>1.71 - ≤ 3.42 mmol/L >3.42 - ≤ 5.7 mmol/L >5.7 - ≤ 11.4 mmol/L >11.4 mmol/L	CTCAE grade 1-4
Glucose	Hypoglycemia <3.0 - ≥ 2.2 mmol/L <2.2 - ≥ 1.7 mmol/L <1.7 mmol/L Hyperglycemia >ULN - ≤ 8.9 mmol/L >8.9 - ≤ 13.9 mmol/L >13.9 - ≤ 27.8 mmol/L >27.8 mmol/L	CTCAE grade 1-4 CTCAE grade 1-4
Albumin	<35 - ≥ 30 g/L	CTCAE grade 1-3

	<30 – ≥ 20 g/L <20 g/L	
Amylase	>ULN - ≤ 1.5 x ULN >1.5 – ≤ 2.0 x ULN >2.0 – ≤ 5.0 x ULN >5.0 x ULN	CTCAE grade 1-4
Lipase	>ULN - ≤ 1.5 x ULN >1.5 – ≤ 2.0 x ULN >2.0 – ≤ 5.0 x ULN >5.0 x ULN	CTCAE grade 1-4
Direct bilirubin	>ULN - ≤ 1.5 x ULN >1.5 – ≤ 2 x ULN >2 – ≤ 3 x ULN >3 – ≤ 10 x ULN >10 x ULN	Same Criteria as Total Bilirubin No CTCAE Not in DILI Guidance
GGT	>ULN - ≤ 2.5 x ULN >2.5 – ≤ 5.0 x ULN >5.0 – ≤ 20.0 x ULN >20.0 x ULN	CTCAE grade 1-4
Calcium	Hypercalcemia >ULN - ≤ 2.9 mmol/L >2.9 – ≤ 3.1 mmol/L >3.1 – ≤ 3.4 mmol/L >3.4 mmol/L	CTCAE grade 1-4
	Hypocalcemia <LLN - ≥ 2.0 mmol/L <2.0 – ≥ 1.75 mmol/L <1.75 – ≥ 1.5 mmol/L <1.5 mmol/L	CTCAE grade 1-4
Magnesium	Hypermagnesemia >ULN - ≤ 1.23 mmol/L >1.23 – ≤ 3.30 mmol/L >3.30 mmol/L	CTCAE grade 1, 3, 4 No CTCAE grade 2
	Hypomagnesemia <LLN - ≥ 0.5 mmol/L <0.5 – ≥ 0.4 mmol/L <0.4 – ≥ 0.3 mmol/L <0.3 mmol/L	CTCAE grade 1-4
Inorganic phosphate	Hypophosphatemia <0.74 – ≥ 0.6mmol/L <0.6 – ≥ 0.3 mmol/L <0.3 mmol/L	CTCAE grade 1-4
ALT	>ULN - ≤ 3 xULN >3 – ≤ 5 xULN >5 – ≤ 8 xULN >8 – ≤ 20.0 xULN >20.0 x ULN	Per FDA DILI Guidance Jul 2009 and CTCAE
AST	>ULN - ≤ 3 xULN >3 – ≤ 5 xULN >5 – ≤ 8 xULN >8 – ≤ 20.0 xULN	FDA DILI Guidance and CTCAE

	>20.0 x ULN	
ALT or AST	(ALT>ULN and ALT ≤ 3 xULN) or (AST>ULN and AST ≤ 3 xULN) (ALT>3 xULN and ALT ≤ 5 xULN) or (AST>3xULN and AST ≤ 5 xULN) (ALT>5 xULN and ALT ≤ 8 xULN) or (AST>5xULN and AST ≤ 8 xULN) (ALT>8 xULN and ALT ≤ 20 xULN) or (AST>8xULN and AST ≤ 20 xULN) ALT>20 xULN or AST> 20 xULN	FDA DILI Guidance
Alkaline Phosphatase	>ULN - ≤ 1.5xULN >1.5 – ≤ 2.5 xULN >2.5 – ≤ 5.0 x ULN >5.0 – ≤ 20.0 x ULN >20.0 x ULN	FDA DILI Guidance and CTCAE
Total Bilirubin	>ULN - ≤ 1.5 x ULN >1.5 – ≤ 2 x ULN >2 – ≤ 3 x ULN >3 – ≤ 10 x ULN >10 x ULN	FDA DILI Guidance and CTCAE
ALT and Total Bilirubin	ALT>3xULN and TBILI>2xULN	FDA DILI Guidance Jul 2009
AST and Total Bilirubin	AST>3xULN and TBILI>2xULN	FDA DILI Guidance Jul 2009
(ALT or AST) and Total Bilirubin	(ALT>3xULN or AST>3xULN) and TBILI>2xULN	FDA DILI Guidance Jul 2009
Hematology		
WBC	WBC decreased <LLN - ≥ 3.0 x 10e9 /L <3.0 – ≥ 2.0 x 10e9 /L <2.0 – ≥ 1.0 x 10e9 /L <1.0 x 10e9 /L	CTCAE grade 1-4
	Leukocytosis >100 x 10e9 /L	CTCAE grade 3 (only Grade available)
Lymphocytes	Lymphocyte decreased <LLN - ≥ 0.8 x10e9 /L <0.8 – ≥ 0.5 x10e9 /L <0.5 – ≥ 0.2 x10e9 /L <0.2 x10e9 /L	CTCAE grade 1-4
	Lymphocyte increased >4 – ≤ 20 x10e9/L >20 x10e9/L	CTCAE grade 2, 3 (only Grades available)
Neutrophils	Neutrophil decreased <LLN - ≥ 1.5 x10e9 /L <1.5 – ≥ 1.0 x10e9 /L <1.0 – ≥ 0.5 x10e9 /L <0.5 x10e9 /L	CTCAE grade 1-4
Hemoglobin	Hgb decreased (anemia) <LLN - ≥ 100 g/L <100 – ≥ 80 g/L < 80 g/L	CTCAE grade 1-3
	Hgb increased >ULN - ≤ 20 g/L above ULN >20 g/L above ULN - ≤ 40 g/L above ULN >40 g/L above ULN	CTCAE grade 1-3

Platelets	Platelet decreased	CTCAE grade 1-4
	<LLN - $\geq 75.0 \times 10^9 /L$	
	<75.0 - $\geq 50.0 \times 10^9 /L$	
	<50.0 - $\geq 25.0 \times 10^9 /L$	
	<25.0 $\times 10^9 /L$

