9.4.1.5 Clinical Laboratory

The analysis of clinical laboratory measurements will be presented separately for the Ivacaftor Run-in Period and by treatment group at each scheduled time point for the Active Comparator Treatment Period based on the corresponding Safety Set.

For treatment-emergent laboratory measurements, the raw values and change from baseline values of the continuous hematology and chemistry results, including coagulation studies will be summarized in SI units by treatment group and visit.

The number and percentage of subjects with at least 1 potentially clinically significant (PCS) laboratory event during the TE period will be summarized overall and by treatment group, including the shift of the PCS event from baseline to postbaseline. The PCS criteria are provided in [Appendix I](#).

For each liver function test (LFT) laboratory test (alanine aminotransferase [ALT], aspartate aminotransferase [AST], alkaline phosphatase [ALP], gamma-glutamyl transferase [GGT], and total bilirubin), the following additional analyses will be conducted for the Active Comparator Treatment Period:

- A listing of subjects with elevated LFT results during the TE period will be presented. For each subject in the listing, LFT assessments at all time points will be included (scheduled and unscheduled).
- For each of the LFTs, mean values (±SD) will be plotted by visit, and a box plot of the LFT value/ULN will be plotted by visit.
- The incidence of LFTs meeting threshold criteria
- For each of the LFTs, mean values (±SD) will be plotted by visit, and a box plot of the LFT value/ULN will be plotted by visit.
- The incidence of LFTs meeting threshold criteria against the baseline threshold criteria also will be summarized by treatment group, LFT parameters, and visit (only shifts to values worse than baseline will be presented).

- A scatter plot of the maximum ALT value across visits versus the maximum total bilirubin value also will be presented. The ALT and total bilirubin values will be presented on a logarithmic scale. The graph will be divided into 4 quadrants with a vertical line corresponding to 3xULN for ALT and a horizontal line corresponding to 2xULN for total bilirubin. A similar graph of maximum AST value versus maximum total bilirubin value will be presented as well.

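### In SAP Appendix I the hypoglycemia and hypophosphatemia rows list three bands for four stated CTCAE grades; the mildest band was most likely left out

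*SAP*

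**What the plan says.** Protocol 12.3.4.2 leaves the PCS criteria to the SAP. SAP 9.4.1.5 plans the summary: "The number and percentage of subjects with at least 1 potentially clinically significant (PCS) laboratory event during the TE period will be summarized overall", and also by treatment group, with the shift in PCS status from baseline. It refers to Appendix I for the criteria.

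The glucose row of Appendix I begins "Hypoglycemia <3.0 - ≥ 2.2 mmol/L <2.2 - ≥ 1.7 mmol/L <1.7 mmol/L Hyperglycemia >ULN - ≤ 8.9 mmol/L" and goes on to three further high-glucose bands. The comment column gives one label for each direction: "CTCAE grade 1-4 CTCAE grade 1-4". The inorganic phosphate row reads "Hypophosphatemia <0.74 – ≥ 0.6mmol/L <0.6 – ≥ 0.3 mmol/L <0.3 mmol/L" and is also labelled as grades 1 to 4.

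Other rows with three bands have a label that accounts for it. Low sodium is marked "CTCAE grade 1, 3, 4 (No CTCAE grade 2", and low potassium "CTCAE grade 1&2, 3, 4 (Grade 1 and 2 are the same". A complete four-band decrease row looks like low magnesium: "Hypomagnesemia <LLN - ≥ 0.5 mmol/L <0.5 – ≥ 0.4 mmol/L <0.4 – ≥ 0.3 mmol/L <0.3 mmol/L".

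**The concern.** Three bands cannot carry four grades, so in these two rows either a band or the label is wrong. Appendix I is the only definition that the programmer of the PCS tables has for glucose and phosphate. Both analytes are in the serum chemistry panel (Protocol Table 11-2), which Protocol Table 3-2 schedules at every visit from Week -4 onward. The ambiguity therefore runs through both treatment periods and both arms.

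Two things are at stake. If the mildest band is the missing one, mildly low values may fall in no band, so they produce neither an event nor a shift in the summary by treatment group. And because the grade of each band is not printed, two programmers could number the same three bands differently.

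**Working it through.** **Inputs.** Bands and labels come from SAP Appendix I. The rows taken are those whose comment names CTCAE grades, with increase and decrease counted separately: 27 rows. Rows with no grade numbers are left out: ALT, AST, alkaline phosphatase and total bilirubin, the combined liver criteria, and blood urea nitrogen and direct bilirubin, which are marked as having no CTCAE grading.

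**Step 1: band count against label.** Of the 27 rows, 19 are labelled with four grades.

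| Rows labelled with four grades | Number | Bands printed |
|---|---|---|
| Low glucose, low phosphate | 2 | 3 each |
| All others | 19 − 2 = 17 | 4 each |

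The remaining 27 − 19 = 8 rows (low sodium, low potassium, high magnesium, albumin, low and high hemoglobin, high WBC, high lymphocytes) have fewer bands and a label that matches. The mismatches are therefore 2 of 27.

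**Step 2: which band is likely absent.** Apart from glucose and phosphate, six decrease rows are labelled 1 to 4: calcium, magnesium, WBC, lymphocytes, neutrophils and platelets. All six have four bands, and in all six the first starts at the LLN. Glucose and phosphate start at fixed cuts, 3.0 and 0.74 mmol/L.

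The printed bands are also contiguous and open at the bottom: 3.0, 2.2, 1.7 and below for glucose; 0.74, 0.6, 0.3 and below for phosphate. No interval below the first cut is uncovered. If a whole band is missing, it must lie above the first cut, which makes it the mildest band.

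**Step 3: effect of numbering the printed bands 1, 2, 3.** The under-grading depends on why there are only three:

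| Reason for three bands | Correct grades of the printed bands | Steps too mild |
|---|---|---|
| Grade 1 band omitted | 2, 3, 4 | 1, 1, 1 |
| Grades 1 and 2 share the first band | 1 or 2, 3, 4 | 0 or 1, 1, 1 |
| Grade 2 does not exist | 1, 3, 4 | 0, 1, 1 |
| No separate grade 4 band | 1, 2, 3 | 0, 0, 0 (grade 4 never assigned) |

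**Step 4: width of the uncounted interval if grade 1 was omitted.** Width = LLN − first cut. The documents give no LLN, so the values below are assumptions.

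| Glucose LLN (mmol/L) | LLN − 3.0 | Phosphate LLN (mmol/L) | LLN − 0.74 |
|---|---|---|---|
| 3.0 | 0 | 0.74 | 0 |
| 3.3 | 0.3 | 0.78 | 0.04 |
| 3.6 | 0.6 | 0.81 | 0.07 |
| 3.9 | 0.9 | 0.87 | 0.13 |

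**The case against.** **The missing band is inferred.** The documents do not reproduce the CTCAE cut-offs. The same appendix has three-band rows that arise from a skipped grade and from merged grades, and a correct set of bands with a wrong comment would look the same. This stands: the mismatch is certain, while the omitted grade 1 band is a strong inference from the pattern of the other rows.

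**A fixed starting cut is not itself an error.** Albumin, triglycerides and raised lymphocytes also start at fixed values. This stands too. A reader might infer that values just below normal are certainly uncounted. The documents do not support that without an LLN: if the phosphate LLN is 0.74 mmol/L or lower, no low value is missed.

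**Under-grading is conditional.** A reader might infer that events will be graded too mildly. SAP 9.4.1.5 plans PCS counts and shifts and does not tell anyone to number the bands. Grades appear only in the comment column, and adverse event severity is graded separately by the investigator (Protocol 13.1.1.4).

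**High WBC.** A reader might see a similar gap in "Leukocytosis >100 x 10e9 /L", the only criterion for raised WBC. The comment on that row says that this is the one grade available, so row and label agree and no change is warranted.

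**Lost text.** A line lost in converting the PDF cannot be fully excluded. Losing a line in each of two separate rows, with the rest of each row intact, is unlikely.

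**Small impact.** Safety is descriptive, without testing (SAP 9.4). Raw values and changes are summarized, and out-of-range chemistry values are listed (SAP 9.4.1.5). This limits the consequence, but a listing does not repair a count by treatment group.

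**Conclusion.** The hypoglycemia and hypophosphatemia rows are wrong as written: three bands against four stated grades, the only two such mismatches among 27 rows. The most likely cause is that the grade 1 band was left out.

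On that reading, and with an LLN above 3.0 mmol/L (glucose) or 0.74 mmol/L (phosphate), low values above the first cut count as no PCS event and no shift. For the LLN values assumed above, the interval is 0 to 0.9 mmol/L wide for glucose and 0 to 0.13 mmol/L for phosphate. How many subjects would fall in it cannot be said from the documents. If the bands were also numbered in order, each event would be graded one step too mild.

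The consequence is confined to descriptive safety counts and shifts; no efficacy result depends on these rows. Because the correction can change reported counts by arm, it is more than a typographical matter and worth making before database lock.

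**What to change.** In SAP Appendix I:

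- Check both rows against the CTCAE version used for laboratory grading, and name that version. The appendix gives none; Protocol 13.1.1.4 names Version 4.0 for adverse event severity.
- If the check confirms an omitted grade 1 band, add a first band from below the LLN down to 3.0 mmol/L inclusive for glucose, and from below the LLN down to the verified first cut for phosphate. The printed bands then become grades 2, 3 and 4.
- If the check shows that the bands are complete, correct the label instead, with a note like those for sodium and potassium.
- In either case, print the grade beside each band.

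The cost is about one line per row in the appendix and the matching change in the laboratory grading program. No new data are needed. If a band is added, counts of low glucose and low phosphate can only stay the same or rise. SAP section 4 has the plan finalized before database lock; a later change would have to be documented in the clinical study report.
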